## 1.0 Objectives

### 1.1 Purpose/Objectives.

Cardiac Rehabilitation (CR) is approved for patients with acute myocardial infarction (AMI)/acute coronary syndrome (ACS), coronary artery bypass surgery (CABG), percutaneous coronary intervention (PCI), stable ischemic heart disease (IHD), heart valve repair (surgical or transcatheter), heart failure (HF), and peripheral arterial disease (PAD). Yet, participation in CR is low in older adults (~13% nationally), despite their being at greatest risk for harm from the dangers associated with cardiovascular disease (CVD) in old age.

Studies on CR participation among older adults cite a lack of systematic referral, delays in starting CR following hospitalization, difficulty in finding programs that are convenient and accessible, competing time demands from family, and costs of copayments as some of the reasons that CR is poorly utilized. Yet, steps to automate referral, moderate costs, and simplify access have not solved underutilization. Further, home-based, hybrid, and tele-health have been promoted as enrichments to CR, but adherence in these programs has often been low and the utility of these new formats for older adults with complex medical and geriatric challenges remains poorly explored. [name] developed principles and infrastructure for a Modified Application of Cardiac Rehabilitation for Older Adults (MACRO) at the VA Pittsburgh Healthcare System (VAPHS) with the effect that participation in CR increased from <3% to ~64% (mean age 69 years). MACRO was designed to address the idiosyncratic needs of older adults, and to facilitate successful implementation of CR for this population. The goal of this trial is to more definitively study the utility of the MACRO intervention.

A key significance of MACRO is the expanded concept of risk. Aging physiology predisposes to CVD but also to disablement, multimorbidity, sarcopenia, frailty, cognitive impairment, and sensory deficiencies. CVD accelerates frailty, disability, and cognitive decline. Whereas risk is traditionally defined in respect to metrics oriented to the heart and CVD (and standardized as such by the American Association of Cardiovascular and Pulmonary Rehabilitation [AACVPR]), MACRO broadens the approach to assessment with additional functional and frailty criteria. In other words, AACVPR criteria do not provide a full assessment of risk, since functional risk are distinct, and also predict poor cardiovascular outcomes, as well as risks of frailty and disability. To address this additional dimension of functional risk, the MACRO intervention impacts common geriatric challenges using comprehensive risk assessment and coordinated strategies to tailor CR to address these risks.

### Specific Aims/Hypotheses

**Aim 1:** To establish efficacy, safety and acceptability of the MACRO intervention via a RCT.

We hypothesize that after 3 months, compared to standard of care (SOC), participants randomized into the MACRO arm will have:

H1.1: Greater improvements in function as measured by Activity Measure for Post-Acute Care Computer Adaptive Test (AM-PAC-CAT) Basic Mobility Domain (primary outcome).

H1.2: Greater improvements in function as measured by accelerometry; AM-PAC CAT Daily Activity Domain; depression; frailty; self-efficacy; and quality of life. These will be collected to the extent possible in respect to local limitations that may result from fluctuations in COVID-19 prevalence.

H1.3: Greater CR participation and adherence.

H1.4: Greater impact in readmissions and hospitalization.

**Aim 2:** To examine the duration of benefit of MACRO compared to SOC.

H2.1: We hypothesize that relative MACRO benefits (i.e., function indices (see H1.2), adherence and readmissions/hospitalization will persist after 6 and 12 months (12 months will be captured as timing allows)

**Aim 3:** To explore characteristics of patients who benefit the most from the MACRO intervention.

H3.1: We anticipate functional capacity and other baseline characteristics will identify those who benefit from the MACRO intervention (exploratory).

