**Table 1. Data Collection Plan**

Study Measure	Baseline	3, 6, 12 months
Risk assessment	X	
AM-PAC CAT Basic Mobility Domain (primary outcome)	X	X
Accelerometer	X	X
AM-PAC CAT Daily Activity Domain	X	X
3 Day Food Record (not at WU site)	X	X
Questionnaires	X	X
CR adherence/attendance		X
Reduced falls, medication burden, readmissions and hospitalization	X	X

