to robust). AM-PAC allows for the examination of perceived difficulty and level of assistance/limitations in 3 domains – Basic Mobility (**primary outcome**), Daily Activity, and Applied Cognition, building on Item Response Theory (IRT). AM-PAC- combines items from existing instruments into one scale, and ranks them according to level of difficulty for each of the 3 domains. IRT assumes that all items within a domain measure a single concept and are independent. In this study the Basic Mobility domain will be the primary outcome, and the Daily Activity domain will be one of the secondary outcomes.

- E. **Self-efficacy:** Higher self-efficacy correlates to greater capacity and duration for physical activity and independence. For this study we rely on the 13-item self-efficacy scale developed by Sullivan, et al.
- F. **Quality of Life (QoL):** RAND-12 is a 12-item scale developed to evaluate QOL.
- G. **Falls:** Falls are a common, deleterious, and expensive aspect of aging which may be preventable via the tenets of MACRO such as good transitional care, age-appropriate exercise, and de-prescribing. We will measure falls as follows: at baseline, we will ask, “Have you had any falls in the past 3 months?” In follow-up assessments, we will ask about interim falls, as well as their severity (e.g., if they caused injury).
- H. **Deprescribing-Eligible Medications (DEMs):** DEMs are medications that are potentially deleterious for participants. These medications are pre-identified, based in part on the Beers Criteria and in part based on CR-specific risks of falls.
- I. **Readmissions:** At follow-up assessments, we will ascertain whether the participant had any hospital admissions or other care (e.g., ER visits).
- J. **Institutionalization:** At follow-up assessments, we will ascertain whether the participant required a brief or long-term institutionalization (e.g., Assisted Living, Skilled Nursing Facility [SNF] or inpatient rehabilitation).

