**CDC Check for Safety Check list:**

Participants in the MACRO Intervention arm may receive a Home Fall Prevention Checklist for Older Adults. This check list will be utilized to provide the participant the opportunity to be better informed about safety. The check list may be sent when direct home assessments are not completed.

**MACRO De-Prescribing:** All participants in MACRO will have their medications reviewed to identify DEMS (deprescribing eligible medications). DEMs worsen functional recovery, impair cognitive function, and increase medical risks (falls, bleeding). For participants in the MACRO Intervention arm, opportunities for de-prescribing will be reviewed and specific recommendations will be conveyed to the participant's clinician to optimize recovery (optimizing physical function, minimizing confusion, reducing falls).

Deprescribing assessments will be conducted during the baseline assessments as part of a medication review. Communication will then be initiated with the MACRO participant's primary provider. DEMs have been selected based on goals to optimize function, reduced sedation, and minimize falls.

If DEMS are deprescribed, a standardized approach of follow-up assessments will be implemented to ensure deprescription is well tolerated.

**MACRO arm personalized nutrition:** Older CVD patients are particularly prone to sarcopenia, frailty, and associated vulnerabilities such as exercise intolerance, falls, and poor QOL. A high-quality diet and increased protein intake have been shown to be advantageous in these vulnerable adults. The MACRO Intervention participants will be strongly encouraged to meet with a registered dietitian and receive dietary recommendations that will account for sarcopenia, underweight, overweight, and specific dietary restrictions associated with comorbid conditions (e.g., DM, renal disease) and medications. Nutrition education and facilitation will be optimized in MACRO. The MACRO Intervention participants will be strongly encouraged to meet with a registered dietitian and receive dietary recommendations that will account for sarcopenia, underweight, overweight, and specific dietary restrictions associated with comorbid conditions (e.g., DM, renal disease) and medications. Nutrition education and facilitation will be optimized in MACRO.

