**MACRO Intervention arm telephone intervention.** MACRO staff will contact participants randomized to the MACRO arm approximately once each week until the completion of phase II after which approximately monthly phone calls will be completed. A subset of telephone calls will have a second MACRO staff member listening to calls to enable additional monitoring. The components of each session recorded on the checklist.

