- F. Data and Safety Monitoring Board (DSMB).** The DSMB will meet approximately every six months or as decided by the DSMB. The DSMB will meet to review and approve the protocol prior to beginning data collection. They will decide on specific stopping criteria for the study. The biostatistician and data manager will work closely with the DSMB to provide reports in an acceptable format. Serious Adverse events (SAE) / Adverse events will be monitored continuously throughout the study and will be reported to the DSMB and IRB according to pre-specified requirements. SAE/AE rates and interim study results will be reviewed and discussed by the DSMB at the DSMB meetings.

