## **7.5     *Source records that will be used.***

Sources of material. Primary and secondary outcome measures that will be collected for this study include the AM-PAC CAT, accelerometry, cognitive assessment, depression, frailty, IADLs, readiness for change, adherence, self-efficacy, falls, medication assessment, readmissions, institutionalization.

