**Aim 1 Analysis**-We will fit a series of linear mixed models using the SAS® MIXED procedure with baseline to follow-up changes in continuous outcomes as the dependent variable; intervention arm (MACRO/SOC), follow-up time point (3/6/12 months) and their interaction term as the fixed effects of interest; the baseline value of the continuous outcome as a fixed effect covariate; and a participant random effect to account for multiple measurements over time from the same participant. We will appropriately construct means contrasts to estimate MACRO vs SOC at each follow-up time point. The magnitude and statistical significance at  $\alpha=0.05$  of the MACRO vs SOC difference at 3 months for AM-PAC CAT Basic Mobility Domain will serve as the formal test of the primary hypothesis H1.1. If significant, we will define a meaningful responder as having at least a 2.60 point improvement in AM-PAC CAT Basic Mobility Domain over 3 months, compute percentage of responders in both arms, and conclude a number-needed-to-treat (NNT) as the reciprocal of the difference in percentages. We will employ the same analytic strategy described above for each of our secondary continuous outcomes such as physical activity, depression, frailty, self-efficacy and quality of life (H1.2). For the secondary outcomes measured only once at 3 months such as participation, adherence and satisfaction (H1.3), we will consider using Wilcoxon rank sum, chi-square and Fisher's exact tests to make between-intervention comparisons, depending on the categorical/ordinal/interval nature of the outcomes and their propensity for ill-behaved distributional properties. For count outcomes such as falls, number of medications, readmissions and hospitalizations in H1.4, we will fit a series of negative binomial regression models with the count outcome as the dependent variable; exposure time for the counts as an offset; a log link function; and intervention arm as the main independent factor of interest; and a marker of history of the outcome at baseline as a covariate MACRO vs SOC incident rate ratio and its statistical significance will serve as tests of H1.4.

**Aim 2 Analysis**-In the linear mixed models described above for H1.1 and H1.2, we will examine the between-intervention means contrasts at 6- and 12-months. The magnitude and statistical significance of the MACRO vs SOC arm differences at 6 and 12 months will serve as the formal test of the hypothesis H2.1.

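### Aim 1 sets out to establish safety by RCT, but 9.1 C specifies no by-arm comparison of AEs, SAEs or deaths, and no general AE question is listed at the shared follow-up assessments

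*Combined protocol and SAP*

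**What the plan says.** Specific Aims/Hypotheses opens Aim 1 with "To establish efficacy, safety and acceptability of the MACRO intervention via a RCT". None of H1.1 to H1.4 names AEs, SAEs or death, and neither do the endpoints in 6.1.

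The nearest planned analysis is in 9.1 C, Aim 1 Analysis: "For count outcomes such as falls, number of medications, readmissions and hospitalizations in H1.4" are compared by arm with negative binomial models. The matching row of Table 1 reads "Reduced falls, medication burden, readmissions and hospitalization". The outcome list in 7.5 ends with "adherence, self-efficacy, falls, medication assessment, readmissions, institutionalization".

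On collection, 7.2 item I says "At follow-up assessments, we will ascertain whether the participant had any hospital admissions or other care (e.g., ER visits". Items G and J cover interim falls with their severity, and institutionalization. On monitoring, 7.4 F says "Serious Adverse events (SAE) / Adverse events will be monitored continuously throughout the study", with rates reviewed by the DSMB. Section 10.0 refers to a DSMB charter and an AE/SAE SOP; neither is part of the documents.

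The MACRO arm has further contact. Under MACRO De-Prescribing in 7.2, if medications are stopped, "a standardized approach of follow-up assessments will be implemented to ensure deprescription is well tolerated". Under the telephone intervention, "MACRO staff will contact participants randomized to the MACRO arm approximately once each week until the completion of phase II", and about monthly after that.

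**The concern.** An aim that names safety needs a safety comparison. The counts compared in 9.1 C belong to H1.4, which is worded as a benefit hypothesis, and one of them, number of medications, is something the intervention sets out to change. The foreseeable risks in 12.1 range from muscle soreness, light-headedness and chest discomfort to arrhythmia, heart attack and stroke. Under the plan, an event of this kind that leads to admission is compared only as a hospitalization. A non-serious event, or a death outside hospital, enters no specified comparison.

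Collection is the harder problem, because an analyst can add a table later but cannot recover events that nobody asked about. If MACRO participants speak to study staff most weeks and SOC participants have no matching schedule, staff have more chances to hear of minor events in MACRO. A higher AE rate in MACRO, seen by the DSMB or in the final report, could then be harm or extra detection, and the data would not show which.

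**Working it through.** **1. The plan's own figure.** The documents give no figure for safety. The sample size in 9.1 D supplies the denominators, so I checked it first. Inputs: difference 2.60, SD of change 7.97, two-sided alpha 0.05, power 80%.
- n per arm = 2 × (1.96 + 0.8416)² × 7.97² / 2.60² = 147.5, so 148. The t-test version gives 148.5, so 149, as stated.
- 149 / 0.80 = 186.25, so 187 per arm and 374 in all, as stated.

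**2. Where a safety comparison could appear.**
- H1.1 to H1.4: function and other patient measures, participation, readmissions and hospitalization. No AE, SAE or death.
- 6.1 endpoints: the same.
- Table 1 and 7.2 items A to Q: falls with severity, admissions and ER visits, institutionalization, and medications. No general AE item.
- 7.5 outcome list: no AE or death item.
- 9.1 C: falls, number of medications, readmissions and hospitalizations by arm. The list is introduced as examples, so it is open, but no AE, SAE or death item is in it. ER visits and institutionalization are collected but not named.

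**3. Contact after baseline.**
- Both arms: assessments at 3, 6 and 12 months (12 as timing allows), done by blinded assessors.
- Either arm, no schedule given: calls to track CR sessions (7.2 L) and possible calls about accelerometer return (7.2 K).
- MACRO only: about weekly calls through phase II, then about monthly, plus tolerance follow-up after deprescribing.
- SOC only: none described. Section 7.3 C says that the SOC group controls for regular study contact, but gives no schedule of calls.

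The length of phase II is not given. If it is 8 to 12 weeks (assumed), MACRO has 8 + 1 = 9 to 12 + 0 = 12 scheduled calls by week 13, and 8 + 4 = 12 to 12 + 3 = 15 by week 26.

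**4. Precision of a by-arm comparison.** The half-width of the 95% CI for a difference in proportions is 1.96 × √(2p(1 − p)/n). The event proportion p is assumed, as the documents give none.

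| p | n = 187 per arm | n = 149 per arm |
|---|---|---|
| 10% | 6.1 points | 6.8 points |
| 20% | 8.1 points | 9.1 points |
| 40% | 9.9 points | 11.1 points |

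For p = 20% and n = 187: 1.96 × √(0.32/187) = 0.081. The comparison can bound an excess of events but cannot exclude a modest one.

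**The case against.** The strongest reply is that much of this is covered. Falls with injury, admissions, ER visits and institutionalization are asked of both arms and capture many AEs and SAEs; falls, readmissions and hospitalizations are compared by arm. The 9.1 C overview says that data will be summarized by treatment group, and the CONSORT diagram is to give reasons for missing data, where deaths should surface. The DSMB reviews SAE and AE rates, and 9.1 B requires a cumulative adverse-event summary for the IRB. How AEs are collected is normally set out in an SOP, and one exists.

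Most of this stands. It means that the missing table alone would be a small matter, since an analyst would probably supply it. It does not settle collection. DSMB review is interim oversight, and the IRB summary is not stated to be by arm. The supplied text does not show that both arms are asked the same AE questions.

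A reader might go further and infer any of the following, which the documents do not support:
- That no AE-related question is asked at follow-up. Items G, I and J of 7.2 are such questions.
- That the follow-up assessments are the arms' only shared contact. Baseline is shared, and CR-tracking calls are not limited to one arm.
- That AE rates will be inflated in MACRO by some stated amount. No capture rates are given, the calls are described as supporting CR, and nothing says that they feed AE reports.
- That the planned 20% dropout shows how many safety data will be lost for Aim 1. Section 17.0 ties that figure to 52 weeks, whereas Aim 1 is set at 3 months.

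**Conclusion.** The point holds in a limited form. Safety is a stated aim of the randomized comparison, yet 9.1 C specifies no by-arm comparison of AEs, SAEs or deaths as such, and no general AE question is listed on the schedule that both arms share. Scheduled contact is heavier in MACRO, so AE rates by arm could differ through detection alone. The size of that effect cannot be derived, and it is nil if the SOP or charter already makes ascertainment equal. The conclusion rests on the supplied text being complete about what is asked at assessments and silent about what the SOP requires. The primary test and the sample size are unaffected. The change is worth making because it is cheap and because collection cannot be repaired after the trial.

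**What to change.** Add a safety paragraph to 9.1 C under Aim 1, with three parts.

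1. **Same questions in both arms.** At the existing 3, 6 and 12-month assessments, the blinded assessor asks every participant a short fixed set of AE questions, after the AM-PAC. The by-arm comparison of non-serious AEs uses these answers: number and percentage with an event, rate, and arm difference with 95% CI.
2. **Source of report.** Add a field to the AE form recording how each event came to light. List AEs learned only at MACRO contacts separately, and give the DSMB the same split.
3. **Deaths and SAEs.** Report them by arm in all randomized participants, using the same sources in both arms as far as consent allows. Section 11.0 already provides for asking participants who withdraw whether routine-care data may be collected.

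If the AE/SAE SOP or DSMB charter already does this, a citation in 9.1 C is enough for the collection part, alongside the by-arm report.

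The cost is one SAP paragraph, a few added questions and one form field; no participants are added. Answers may reveal the arm to an assessor. Asking after the AM-PAC protects the 3-month primary endpoint, but leaves a small unblinding risk at 6 and 12 months. Precision stays limited, and 12-month data will be fewer because that visit depends on when a participant enrolled.

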## 2.0 Background

### 2.1 *Relevant experience.*

Prevalence of cardiovascular disease increases with age. Nonetheless, participation in CR decreases with age; only approximately 13% of eligible older patients enroll. CR is indicated for patients with AMI/ACS, CABG/PCI, stable IHD, heart valve repair (surgical or transcatheter), PAD, and/or HF.

Studies on CR participation among older adults cite a lack of systematic referral, delays in starting CR following hospitalization, difficulty in finding programs that are convenient and accessible, competing time demands from family, and costs of copayments as some of the reasons that CR is poorly utilized. Yet, steps to automate referral, moderate costs, and simplify access have not solved underutilization. Further, home-based, hybrid, and tele-health have been promoted as enrichments to CR, but adherence in these programs has often been low and the utility of these new formats for older adults with complex medical and geriatric challenges remains poorly explored.

MACRO is a transformational model of care that shifts CR from a primary focus on CVD, to CR that is centered on patients themselves, i.e., individuals who usually have many age-related problems in addition to CVD. MACRO organizes care relative to patients' goals of care and composite risks. Patients are engaged, assessed for their goals and risks, and education is initiated to best facilitate informed choices regarding realistic and practical strategies. Selection of site-, home-, or hybrid-based care is based on which option will best meet that individual patient's preferences and comprehensive needs.

### 2.2 *Significance of the research.*

#### A. **MACRO is patient-centered CR tailored for older complex patients with CVD.**

A central premise of MACRO is that clinical approaches to older adults with CVD must address more than their cardiovascular issues. MACRO incorporates geriatrics principles in association with CV principles as co-dominant priorities of care.

### 2.3 *Innovation of the research.*

A. MACRO responds to a critical gap in CVD management by melding CR principles with geriatric risk modifying strategies in an intentional and flexible treatment approach. MACRO is designed to optimize accessibility and effectiveness, and to augment the potential for recovery from CVD events that are highly prevalent and otherwise prognostically dire. MACRO constitutes an important advance in geriatric cardiology wherein the conventional approach to CVD care is transmuted and enriched by linking cardiovascular management to the broader complexity of aging.

B. No prior studies have tested the impact of transitions of care in CR

